4.4. Lifestyle Requirements

It is important that subjects continue their typical dietary habits and physical activity throughout the study, ie, from Screening until the on-site follow-up visits. Subjects will be asked not to change their diet and macronutrient composition and/or their exercise routine.

4.4.1. Woman of Childbearing Potential (WOCBP)

A woman is considered fertile following menarche and until becoming postmenopausal unless permanently sterile (see below).

If fertility is unclear (eg, amenorrhea in adolescents or athletes) and a menstrual cycle cannot be confirmed before the first dose of study intervention, additional evaluation should be considered.

Women in the following categories are not considered WOCBP:

1. Premenopausal female with 1 of the following:

- Documented hysterectomy;
- Documented bilateral salpingectomy;
- Documented bilateral oophorectomy.

For individuals with permanent infertility due to an alternate medical cause other than the above, (eg, mullerian agenesis, androgen insensitivity), investigator discretion should be applied to determining study entry.

Note: Documentation for any of the above categories can come from the site personnel's review of the participant's medical records, medical examination, or medical history interview. The method of documentation should be recorded in the participant's medical record for the study.

2. Postmenopausal female:

- A postmenopausal state is defined as no menses for 12 months without an alternative medical cause. In addition:
 - A high FSH level in the postmenopausal range must be used to confirm a postmenopausal state in women under 60 years of age and not using hormonal contraception or HRT.

- A female on HRT and whose menopausal status is in doubt will be required to use one of the nonestrogen hormonal highly effective contraception methods if she plans to continue HRT during the study. Otherwise, they must discontinue HRT to allow confirmation of postmenopausal status before study enrollment.

4.4.2. Contraception

In this study, male subjects and female subjects who are of childbearing potential as applicable to the study will receive PF-06730512, which has been associated with suspected teratogenicity/fetotoxicity.

Female subjects who are, in the opinion of the investigator, sexually active and at risk for pregnancy with their partner(s) must agree to use 1 method of highly effective contraception throughout the study and for at least 63 days after the last dose of PF-06730512. Highly effective methods of contraception are those that result in a failure rate of <1% per year when used consistently and correctly. The investigator or his/her designee, in consultation with the subject, will confirm that the female subject has selected 1 method of highly effective contraception for the individual subject and her partner(s) from the list below, and will confirm that the subject has been instructed in their consistent and correct use. Contraceptive use by men or women should be consistent with local regulations regarding the use of contraceptive methods for those participating in clinical studies.

Male subjects are required to use a condom as protection from the potential risk of exposure via PF-06730512 in the ejaculate which would pose a risk to a developing embryo/fetus in WOCBP. This is purely precautionary as the calculated safety margin for PF-06730512 is ≥ 100 -fold between the estimated maternal exposure due to seminal transfer and the NOAEL for serious manifestations of developmental toxicity in nonclinical studies.

At time points indicated in the [Schedule of Activities](#), the investigator or designee will inform the subject of the need to use 1 highly effective method of contraception consistently and correctly and document the conversation, and the subject's affirmation, in the subject's chart. In addition, the investigator or designee will instruct the subject to call immediately if the use of the selected contraception method is discontinued or if pregnancy is known or suspected in the subject or partner.

Highly Effective Methods That Are User Dependent

Items marked with an asterisk (*) denote contraceptives that are not approved for use in Japan.

1. Implantable progestogen-only hormone contraception associated with inhibition of ovulation.*
2. Intrauterine device.
3. Intrauterine hormone-releasing system.

4. Bilateral tubal occlusion (eg, bilateral tubal ligation).
5. Vasectomized partner:
 - A vasectomized partner is a highly effective contraceptive method provided that the partner is the sole sexual partner of the WOCBP and the absence of sperm has been confirmed. If not, an additional highly effective method of contraception should be used. The spermatogenesis cycle is approximately 90 days.
6. Combined (estrogen- and progestogen-containing) hormonal contraception associated with inhibition of ovulation:
 - Oral
 - Intravaginal*
 - Transdermal*
7. Progestogen-only hormone contraception associated with inhibition of ovulation:
 - Oral*
 - Injectable*
8. Sexual abstinence:
 - Sexual abstinence is considered a highly effective method only if defined as refraining from heterosexual intercourse during the entire period of risk associated with the study intervention. The reliability of sexual abstinence needs to be evaluated in relation to the duration of the study and the preferred and usual lifestyle of the participant.
9. Progestogen-only oral hormonal contraception where inhibition of ovulation is not the primary mode of action.
10. Male or female condom with or without spermicide.
11. Cervical cap, diaphragm, or sponge with spermicide.
12. A combination of male condom with either cervical cap, diaphragm, or sponge with spermicide (double-barrier methods).

4.5. Sponsor's Qualified Medical Personnel

The contact information for the sponsor's appropriately qualified medical personnel for the study is documented in the study contact list located in the Investigator Site Master File.

To facilitate access to appropriately qualified medical personnel on study-related medical questions or problems, subjects are provided with a contact card. The contact card contains, at a minimum, protocol and investigational product identifiers, subject study numbers, contact information for the investigator site, and contact details for a contact center in the event that the investigator site staff cannot be reached to provide advice on a medical question or problem originating from another healthcare professional not involved in the subject's participation in the study. The contact number can also be used by investigator staff if they are seeking advice on medical questions or problems; however, it should be used only in the event that the established communication pathways between the investigator site and the study team are not available. It is therefore intended to augment, but not replace, the established communication pathways between the investigator site and the study team for advice on medical questions or problems that may arise during the study. The contact number is not intended for use by the subject directly, and if a subject calls that number, he or she will be directed back to the investigator site.

5. STUDY TREATMENTS

For the purposes of this study, and per International Conference on Harmonisation (ICH) guidelines, investigational product is defined as a pharmaceutical form of an active ingredient or placebo being tested or used as a reference/comparator in a clinical trial, including a product with a marketing authorization when used or assembled (formulated or packaged) in a way different from the approved form, or when used for an unapproved indication, or when used to gain further information about an approved use (ICH E6 1.33).

For this study, the investigational product is PF-06730512, a lyophilized powder for injection that requires reconstitution with sterile Water for Injection (WFI). This study does not include the use of placebo.

5.1. Allocation to Treatment

Subjects will be enrolled into Cohort 2 or Cohort 3 after approximately 22 subjects have been enrolled into Cohort 1. The sponsor will issue a formal communication to all sites upon transition from one cohort to the next. Allocation of subjects to the respective cohort (1, 2, or 3) will be conducted through the use of an interactive response technology (IRT) system (interactive Web-based response [IWR]). The site personnel (study coordinator or specified designee) will be required to enter or select information including but not limited to the user's identification (ID) and password, the protocol number, and the subject number. The site personnel will then be provided with a cohort assignment, randomization number (enrollment), and dispensable unit (DU) or container number when investigational product is being supplied via the IRT system. The IRT system will provide a confirmation report containing the subject number, randomization (enrollment) number, and DU or container number assigned. The confirmation report must be stored in the site's files.

[figure not shown]
The study-specific IRT reference manual will provide the contact information and further details on the use of the IRT system.

5.2. Subject Compliance

Investigational Product, PF-06730512, will be administered once every two weeks by qualified investigator site personnel at visits indicated in the [Schedule of Activities](#).

5.3. Investigational Product Supplies

CCI

product is intended for intravenous administration. Details of the preparation and administration of the investigational product are outlined in the Investigational Product (IP) Manual.

5.3.2. Preparation and Dispensing

Within this protocol, preparation refers to the investigator site activities performed to make the investigational product ready for administration or dispensing to the subject/caregiver by qualified staff. Dispensing is defined as the provision of investigational product, concomitant treatments, and accompanying information by qualified staff member(s) to a healthcare provider, subject, or caregiver in accordance with this protocol. Local health authority regulations or investigator site guidelines may use alternative terms for these activities.

PF-06730512 lyophilized powder will be reconstituted using sterile WFI. The investigational product will be prepared at the investigational site or at a site-contracted qualified pharmacy by two operators; one of whom should be a licensed healthcare professional, preferably a qualified pharmacist. The operators must be fully trained and experienced in the reconstitution and preparation of sterile product solutions for intravenous administration. Dose preparation will be performed with locally accepted sterile handling technique.

5.4. Administration

PF-06730512 will be administered by qualified study site staff as an IV infusion over approximately 60 minutes using a calibrated infusion pump according to the IP Manual. The infusion line is flushed using a sufficient volume of Normal Saline (0.9% sodium chloride) that is greater than or equal to the hold-up volume of the infusion line/set. The flush solution should be administered at the same rate to ensure complete delivery of the dosing solution. The start and stop time of the infusion will be recorded on the case report form (CRF). The infusion stop time should be recorded as the time when the end of the saline flush is complete. The post-infusion observation period for each subject shall be 3 hours for the first 3 doses. The observation period can be decreased to 1 hour after the end of infusion for the subsequent doses, provided that no infusion reactions are noted.

If an arm is used for IV infusion, the opposite arm should be used for the pharmacokinetic/pharmacodynamic (PK/PD) blood sample collections, if possible. Premedication with an antihistamine and acetaminophen is optional and might be provided per investigator judgment. See the IP Manual for detailed instructions on how to administer the investigational product.

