Upon commencement of active treatment with PF-06730512, subjects will be dosed intravenously Q2W for up to 24 weeks, but the primary endpoint result will be based on UPCR from a 24-hour urine collection at Week 13. There will be a maximum of 12 infusions of PF-06730512 within the 24-week Investigational Treatment Period.

Telephone contact visits will be conducted the weeks in between dosing visits to check the subject's overall status, including new or worsening adverse events, changes to concomitant medications, compliance with appropriate contraceptive use, and reminders about upcoming urine collections, when applicable.

The study will investigate up to 3 doses of PF-06730512 in up to 3 cohorts, each consisting of up to approximately 22 subjects. **CCI**

All cohorts will collect the same procedures at the same timepoints, according to the [Schedule of Activities](#). Interim analyses may be conducted

whilst the study is ongoing to determine futility of any evaluated dose, and to inform selection of next dose level to be evaluated ([Section 9.6](#)).

SCHEDULE OF ACTIVITIES

The schedule of activities table provides an overview of the protocol visits and procedures. Refer to the **STUDY PROCEDURES** and **ASSESSMENTS** sections of the protocol for detailed information on each procedure and assessment required for compliance with the protocol.

The investigator may schedule visits (unplanned visits) in addition to those listed on the schedule of activities table, in order to conduct evaluations or assessments required to protect the well-being of the subject.

Visit days and Visit weeks are relative to first dosing day, Week 1 Day 1; listed days are the first days of the upcoming week.

Study Procedures Abbreviations in this Table may be found in Appendix 1: Abbreviations	Screening Period	Lead-in Period		Investigational Treatment Period															Follow-up Period				Early Term ⁱ
		1	2	3	5	7	9	11	13	15	17	19	21	23	25	27	29	33					
Visit Week ^a	-12 to -9	-8	-4	-1	1	2	3	5	7	9	11	13	15	17	19	21	23	25	27	29	33		
Visit Days ^a	-90 to -57	-56	-28	-7	1	8	15	29	43	57	71	85	99	113	127	141	155	169	183	197	225		
Visit Window (days)	-5	± 5	± 5	± 5	± 3	± 3	± 3	± 3	± 3	± 3	± 3	± 3	± 3	± 3	± 3	± 3	± 5	± 5	± 5	± 7			
Informed Consent		X ^b																					
Demography (smoking, alcohol)		X ^b	X																				
Eligibility criteria		X	X ^f		X ^f																		
Medical history		X																				X	

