Visit Week ^a	-12 to -9	-8	-4	-1	1	2	3	5	7	9	11	13	15	17	19	21	23	25	27	29	33		
Visit Days ^a	-90 to -57	-56	-28	-7	1	8	15	29	43	57	71	85	99	113	127	141	155	169	183	197	225		
Visit Window (days)	-5	±5	±5	±5	±3	±3	±3	±3	±3	±3	±3	±3	±3	±3	±3	±3	±3	±5	±5	±5	±7		
CCI																							
		█		█		█		█		█		█		█		█		█		█		█	
		█		█		█		█		█		█		█		█		█		█		█	
		█		█		█		█		█		█		█		█		█		█		█	
		█		█		█		█		█		█		█		█		█		█		█	
Urine reserve aliquot (10 mL from 24-hour collection) ^p		X		X		X		X		X		X		X		X		X	X	X	X	X	
Urine drug test	X ^m																						
Urinalysis, including microscopy	X	X	X	X	X ^c	X	X	X	X	X	X	X	X	X	X	X	X	X	X	X	X		
Urine Containers Distribution	X ^{b,j}	X	X	X	X	X	X	X	X	X	X	X	X	X	X	X	X	X	X	X	X		
Urine Collection Diary Distribution		X																					
Check Completion of Urine Collection Diary				X ^o		X		X ^o		X ^o		X ^o		X ^o		X ^o		X ^o	X ^o	X ^o	X ^o		

- Visit day in study is relative to Day 1.
- Subject written informed consent must be obtained prior to any study procedures taking place. The Screening process will require at least 2 site visits to accommodate at-home urine collection required to confirm eligibility (refer to footnote [j](#)). The subject must be provided with containers for urine collection and comprehensive instructions for the urine collection process at Screening Visit 1. For detailed collection procedures see [Section 7.2.1](#).
- All procedures and assessments should be done before dosing of PF-06730512, except for infusion site assessment, post-infusion electrocardiogram (ECG), and post-infusion PK and cytokine blood sampling (see footnotes [f](#) and [h](#)).
- All physical examinations (full and brief examinations) must include edema assessment and weight. Full physical examination must be completed either at Screening or Week -8 Visit (first day of Lead-in Period); otherwise, brief examinations are performed if findings during previous examination or new/open AEs, at investigator discretion. Height is only measured once at Screening.
- Investigational product (IP) administration will last approximately 60 minutes including the flush for the intravenous (IV) infusion. Post-infusion safety observation period of at least 3 hours is required after the first 3 doses of IP (Weeks 1, 3, and 5). The post-infusion observation period for all remaining IP administrations will be 1 hour (Weeks 7 – 23), provided no safety issues are observed.

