1.3.2. Dose Rationale

CCI

[REDACTED]

CCI

[REDACTED]

[REDACTED]

As there is currently no mechanistic biomarker that can provide the link to pathway modulation, PK/pharmacodynamic (PD) modeling approach was employed for projections of ROBO2-SLIT2 % reduction using a kidney site-of-action model. This incorporates preliminary PK modeling from study C0221001, ROBO2 and SLIT2 biomeasure from FSGS kidney samples, and in vitro binding data. The premise is translation of reduction in ROBO2-SLIT2 binding, and hence signaling, to efficacy ie, proteinuria reduction. **CCI**

[REDACTED]

CCI

[REDACTED]

Planned infusion duration in this study is approximately 1 hour, and the monitoring requirements post-infusion are detailed in [Section 7.1.7](#).

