- Phone call to conduct inquiry about any spontaneously reported AEs by asking the subject to respond to a non-leading question such as "how do you feel?"
- Review concomitant medications;
- Review contraceptive use.

Study Week 7 - Day 43

- Review concomitant medications;
- Perform a physical exam including body weight and edema assessment;
- Review contraceptive use;
- Perform serious and non-serious adverse event monitoring;
- Perform single 12-lead ECG Pre-dose and at the end of infusion within an approximately 45--minute window;
- Obtain vital signs (sitting single PR, BP and body temperature);
- Collect blood sample for pre-dose PK, ADA and NAb;
- Collect blood sample for clinical laboratory test and eGFR;
- Use serum for pregnancy test via test strip as a stat procedure performed locally at the site, in females of child-bearing potential, with the negative result being available prior to the administration of investigational product;
- Intravenously administer of IP per IP Manual;
- Monitor subject for AEs and infusion site reaction for approximately 1 hour post end of infusion;
- Collect urine samples for urinalysis;

- Provide subject with containers for urine collection and explain the urine collection process; request that subject perform 24-hour urine collection and FMV for CCI CCI UPCR before next visit.

Study Week 8 - Day 50 (Telephone Visit)

- Phone call to conduct inquiry about any spontaneously reported AEs by asking the subject to respond to a non-leading question such as “how do you feel?”
- Review concomitant medications;
- Review contraceptive use;
- Remind subject of FMV and 24-hour urine collections prior to next visit.

Study Week 9 - Day 57

- Review concomitant medications;
- Perform a physical exam including body weight and edema assessment;
- Review contraceptive use;
- Perform serious and non-serious adverse event monitoring;
- Obtain vital signs (sitting single PR, BP and body temperature);
- Collect blood sample for clinical laboratory test, eGFR and fasting lipid profile (subjects must be fasting at least 8 hours prior to blood draw with no food or drink except water);
- Use serum for pregnancy test via test strip as a stat procedure performed locally at the site, in females of child-bearing potential, with the negative result being available prior to the administration of investigational product;
- Collect blood sample for pre-dose PK, ADA and NAb;
- CCI [REDACTED]
- [REDACTED]

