7.1.7. Infusion Site Reaction

Infusion site reactions will be assessed according to the [Schedule of Activities](#). Infusion site reactions may include but are not limited to: erythema, induration, ecchymosis, pain and pruritus. The size and severity of infusion site reactions will be assessed and documented.

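### The Section 6.2 visit lists give about 1 hour of post-infusion observation from Week 7 with no condition, so after a missed Week 3 or Week 5 dose they fall short of the 3 hours in Section 5.4

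*Protocol*

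**What the plan says.** Three places in the protocol give the observation time.

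- **Section 5.4 (Administration)** counts doses: "The post-infusion observation period for each subject shall be 3 hours for the first 3 doses". It then permits a reduction: "The observation period can be decreased to 1 hour after the end of infusion for the subsequent doses, provided that no infusion reactions are noted".
- **Schedule of Activities, footnote e**, names both doses and weeks: "Post-infusion safety observation period of at least 3 hours is required after the first 3 doses of IP (Weeks 1, 3, and 5"). For the rest: "The post-infusion observation period for all remaining IP administrations will be 1 hour (Weeks 7 – 23), provided no safety issues are observed".
- **Section 6.2 (Investigational Treatment Period)** goes by visit week. Weeks 1, 3 and 5 list about 3 hours. Each dosing visit from Week 7 to Week 23 carries a line such as "Monitor subject for AEs and infusion site reaction for approximately 1 hour post end of infusion", with no condition attached.

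Section 3.1 fixes the dosing weeks as 1, 3, 5 and every second week up to 23, at most 12 infusions. SAP Table 3 (Section 4.2) foresees subjects who miss a dose without withdrawing, though it names no week. Neither document gives a make-up rule or an observation rule after a missed dose.

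**The concern.** A rule by dose number and a rule by visit week give the same answer only while the two stay aligned. A missed early dose separates them. A site working from the Section 6.2 list would then observe a late second or third dose for about 2 hours less than Section 5.4 requires. The Section 6.2 lines also omit the condition that both Section 5.4 and footnote e attach to the shorter period.

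What is at stake is an operative safety instruction, not the analysis. Nothing else on the visit list makes up the difference. At Weeks 1, 3 and 5, cytokine samples run to 4 hours after the start of an infusion of about 1 hour, so the subject is on site for about 4 − 1 = 3 hours afterwards in any case. No cytokine samples are scheduled from Week 7.

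**Working it through.** The plan states no figure to reproduce, so the check is a count.

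**Inputs.** Dosing weeks (Section 3.1): 1, 3, 5, 7, 9, 11, 13, 15, 17, 19, 21, 23, which is 12 infusions. Required time by dose (Section 5.4): 3 hours for doses 1 to 3. Listed time by week (Section 6.2): about 3 hours at Weeks 1, 3 and 5; about 1 hour at Weeks 7, 9, 11, 13, 15, 17, 19, 21 and 23.

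**Assumption.** A missed dose is skipped and not given at an extra visit.

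**Rule.** An infusion is in conflict if it is among the first three doses received and falls at Week 7 or later. The share is the number in conflict divided by the infusions received.

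| Doses missed | Weeks of first three doses received | In conflict | Infusions received | Share |
|---|---|---|---|---|
| None | 1, 3, 5 | 0 | 12 | 0% |
| Week 3 | 1, 5, 7 | 1 | 11 | 9% |
| Week 5 | 1, 3, 7 | 1 | 11 | 9% |
| Weeks 3 and 5 | 1, 7, 9 | 2 | 10 | 20% |
| Weeks 3 and 7 | 1, 5, 9 | 1 | 10 | 10% |
| Weeks 5 and 7 | 1, 3, 9 | 1 | 10 | 10% |
| Weeks 3, 5 and 7 | 1, 9, 11 | 2 | 9 | 22% |

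The first dose defines Week 1, so only doses 2 and 3 can fall late, and the maximum is two infusions per subject. The shortfall for each is 3 − 1 = about 2 hours.

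**Does footnote e decide the case?** Take a third dose given at Week 7. By the words on doses it is one of the first 3 and needs at least 3 hours. By the bracketed weeks it lies in Weeks 7 to 23 and gets 1 hour. The footnote supports either answer.

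**Do the cross-references decide it?** The introduction to the Schedule sends the reader to the Study Procedures and Assessments "sections of the protocol for detailed information on each procedure and assessment required for compliance with the protocol", while Section 6.2 sends the reader back to the Schedule and Section 7. Neither text is said to prevail.

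**The case against.** The strongest reply is that nothing conflicts in the regimen as written: on schedule, all three texts give 3 hours at Weeks 1, 3 and 5 and 1 hour afterwards. Section 6.2 summarises scheduled visits and refers to the Schedule, where the administration and infusion-site rows both carry footnote e with its safety condition. The weeks in that footnote can be read as merely showing where the first three doses normally fall, so that a late third dose keeps its 3 hours. The Section 6.2 lines say approximately 1 hour and set no maximum, so a site that stays 3 hours breaches nothing. The IP Manual, which was not available, may cover the case. The first-in-human study reported no infusion reactions (Section 1.2.5.1).

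Much of this stands, and it keeps the point minor. It does not remove it. The favourable reading of footnote e is only one of two, and a site that follows the Section 6.2 line literally after a missed early dose gives less time than Section 5.4 requires. The first-in-human evidence is indirect: 59 healthy subjects on active drug, by IV or SC administration.

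A reader might infer more than the documents support:

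- *That no time is stated when the condition for 1 hour fails.* Section 5.4 starts from 3 hours and permits a decrease subject to a proviso. If the proviso fails, the natural reading is that 3 hours stays. What is open is only whether a reaction at an earlier dose counts.
- *That the cross-references lead nowhere.* Section 1.3.2 says "Planned infusion duration in this study is approximately 1 hour, and the monitoring requirements post-infusion are detailed in" Section 7.1.7. That section gives no time but says "Infusion site reactions will be assessed according to the" Schedule, whose rows carry footnote e. The route is indirect but ends at a rule, so this is clerical.
- *That Section 5.4 and footnote e contradict each other because one names infusion reactions and the other safety issues.* Both conditions can be met together.
- *That nine of twelve visits are in conflict.* Nine is the number of lines that omit the condition, not the number of infusions given the wrong time.

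**Conclusion.** The mismatch is real but arises only in particular cases. For a subject dosed on schedule without events, 0 of 12 infusions are in conflict. If the Week 3 or Week 5 dose is missed, one infusion is affected; if both are missed, two are, which is the maximum. Each is listed at about 1 hour against 3 required.

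This assumes that missed doses are skipped. The shares in the table describe one subject with that dosing history and not the trial, because the documents do not say how often doses are missed. No count is given for subjects with a reaction or other safety issue, since the text does not say whether the condition looks back to earlier doses. Severity is minor, and the primary endpoint and its analysis are unaffected.

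**What to change.** Make two changes of wording, by amendment or clarification letter:

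1. **Section 6.2, Weeks 7 to 23:** replace the fixed 1-hour period in the nine monitoring bullets with *for the period required by Section 5.4 and footnote e*.
2. **Footnote e:** replace the fixed weeks with *each of the first 3 doses actually received, whatever the visit week*.

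Keep the existing conditions in full: 1 hour for later doses only if no infusion reactions and no other safety issues are observed; otherwise 3 hours stays. Do not add a rule that restores 3 hours only at the next dose after a reaction, and do not leave other safety issues to the investigator's judgment. Either could weaken the present protection.

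The cost is about 2 extra hours on site per affected infusion. Data collection and analysis do not change.
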